11. DATA COLLECTION AND QUALITY ASSURANCE

MESA Exam 6 and Exam 6A study data will be collected at the individual MESA field centers and transmitted electronically to the Collaborative Health Studies Coordinating Center (CHSCC). The CHSCC is an established coordinating center for many multi-center NIH studies. Methods are in place to transmit encrypted data electronically from the MESA field centers to the CHSCC. The CHSCC database server allows for the maintenance of a large and complex database that may be used to retrieve data and generate reports, or to extract subsets for statistical analysis. The CHSCC will format all data into accessible files that exclude any unique identifier fields for analyses

Laboratory measurements will be performed in the Nutrition and Obesity Research Center (NORC) at the University of Washington, a reference laboratory for several multi-center NIH studies. [name], who directs the NORC analytical core and developed the mass-spectroscopic vitamin D assays used in this trial will oversee all laboratory measurements. Reference materials are run with each batch of vitamin D measurements for evaluation of analytical drift over time. External proficiency testing is performed three times each year in association with the College of American Pathologists to ensure concordance with other clinical laboratories nationwide.

12. PROTECTION OF HUMAN SUBJECTS

12.1. Risks to the subjects

A. Human subjects involvement and characteristics

The purpose of this study is to determine individual level characteristics that modify the biological response to vitamin D₃ treatment. We will conduct a 16-week clinical trial of oral vitamin D₃ (cholecalciferol) therapy *versus* placebo among 1,600 participants from the MESA study, an ongoing NHLBI funded cohort study of cardiovascular disease. Participants will be recruited for this trial from five MESA field centers: Forsyth County, NC; Northern Manhattan and the Bronx, NY; Baltimore City and [name]; Los Angeles, CA; and Chicago, IL. MESA investigators from these field centers are co-investigators in this clinical trial. MESA originally recruited 6,814 adults who identified their race/ethnicity as White/Caucasian, Black/African-American, Chinese, or Spanish/Hispanic/Latino from six U.S. communities between July 2000 and August 2002. MESA excluded individuals who had any previous diagnosis of cardiovascular disease. All MESA participants gave informed consent and Institutional Review Board approval was obtained for each study site.

A total of 3,884 participants attended the 5th MESA examination in 2010 at one of the five field centers described above and are scheduled to return for the 6th MESA exam. The average age of these returning participants is 70.3 years; 44% are Caucasian, 36% are African American, and 55% are female. We are proposing to recruit our ancillary study population of 1,600 MESA participants from the 6th MESA exam.

Exclusion criteria specific to this ancillary study are the use of high dose vitamin D supplements (>1000 IU per day), use of any activated vitamin D analog (i.e. calcitriol), a clinical diagnosis of hyperparathyroidism, kidney dialysis or transplantation, a personal history of kidney stones within the previous 5 years, known clinical history of sarcoidosis, self-reported history of elevated serum calcium levels, or serum calcium greater than 11mg/dl at MESA Exam 1 (2000-2002). Each MESA field center will mail ancillary study materials to eligible participants in advance of Exam 6. These materials will explain the goals and procedures of this ancillary study.

At the time of Exam 6, MESA study personnel will approach potentially eligible subjects, confirm eligibility criteria, explain ancillary study details, and answer relevant questions. MESA personnel will then obtain informed consent for those participants who are found to be suitable and interested in this study. All hands-on recruitment procedures will be performed at the MESA field centers described above within MESA Exam 6.

B. Sources of material

As part of MESA Exam 6, participants will complete a series of interviews and questionnaires regarding their medical and surgical histories, medication use, family history, symptomatology, dietary habits, and socioeconomic status. Exam 6 participants will undergo a brief physical examination, which includes measurements of height, weight, and blood pressure, and will provide fasting blood and urine specimens. DNA was collected at the baseline MESA examination in 2000-2002 among participants who consented to genetic testing. Gentotyping was performed from participant DNA in 2009 on the Affymetrix Genome-Wide Human SNP Assay 6.0 (Affymetrix, Inc., Santa Clara, CA) and in 2012 on the HumanExome BeadChip v1.0 (Illumina, Inc., San Diego, CA).

For this trial we will ask participants to complete a brief questionnaire regarding the amount of time spent outdoors and the amount of body surface that was exposed to sunlight during the previous month. A total of 1.0 ml of collected serum and 1.0 ml of collected urine from Exam 6 will be shipped to the University of Washington Department of Laboratory Medicine for measurement of biomarkers relevant to this ancillary study: serum 25-hydroxyvitamin D, 1,25-dihydroxyvitamin D, 24,25-dihydroxyvitmain D, vitamin D binding globulin, parathyroid hormone, albumin, and creatinine, and urine calcium and creatinine. Study medication will be dispensed to all enrolled participants at Exam 6 (section C, below).

Enrolled participants will return approximately 16 weeks after Exam 6 visit for a single follow-up examination (Exam 6A), which will include (1) return of unused study medication to assess adherence, (2) determination of end-of-study blood pressures, (3) completion of an end-of-study medication inventory, (4) completion of a questionnaire to assess sun exposure during the study, (5) collection of blood and spot urine samples. (6) DNA and RNA will be collected to complete transcriptomic analysis to explore epigenetic modifications that modify the biologic response to vitamin D₃ supplementation. Subsequently, we will mail results of serum 25-hydroxyvitamin D and calcium testing before and after vitamin D₃ treatment. Participants will then continue to be followed within the parent MESA study.

C. Study intervention

Pharmacies at each MESA field center will dispense the vitamin D₃ study medication (cholecalciferol; 2,000 IU per day) or matching placebo in a 3:1 ratio at MESA Exam 6. Cholecalciferol and matching placebo will be purchased from Carlson labs (JR Carlson Laboratories, Arlington Heights IL). All study participants will be treated for 16 weeks.

Cholecalciferol is the most widely available and commonly used vitamin D supplement and can be purchased over the counter. The dose of 2000 IU daily is consistent with that used by a number of ongoing, large-scale clinical trials of vitamin D₃. This dose effectively raises vitamin D stores and can be added to pre-existing low-dose vitamin D supplements, including those

contained in multivitamins, while maintaining total daily vitamin D dose within the Tolerable Upper Intake Level (4000 IU daily), defined by the Institute of Medicine as the highest level of nutrient intake that is likely to pose no risk of adverse health effects for almost all individuals in the general population.

D. Potential risks

The short-term, oral vitamin D₃ treatment regimen proposed has been well studied and has minimal safety concerns. Vitamin D₃ can modestly raise urinary calcium levels and some (but not all) studies have observed a small increase in the long-term risk of kidney stones, prompting our exclusion of individuals who have a prior history of stones. Vitamin D₃ supplementation at the doses proposed does not generally affect serum calcium levels.

The ancillary study will utilize previously collected MESA data and stored specimens. The principal risk is the potential loss of confidentiality, which is addressed by procedures at the MESA coordinating center (see section 2, below).

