	Exclusion criteria 
1. Current use of >1,000 international units (IU) of cholecalciferol daily2. Current use of any activated vitamin D product (calcitriol, paricalcitol, hectorol)3. Known history of allergy or adverse reaction to vitamin D treatment4. Known clinical history of primary hyperparathyroidism5. Known clinical history of kidney stones within the previous 5 years6. Known clinical history of kidney dialysis or transplant.7. Known clinical history of sarcoidosis8. Self-reported history of having elevated serum calcium levels9. Serum calcium level >11 mg/dl at MESA Exam 1 (2000-2002)10. Current participation in another interventional study11. Inability to provide written informed consent
Study Duration	16 weeks
Treatment, Dosage, and Route of Administration	2,000 IU cholecalciferol or inactive placebo taken by mouth once daily
Efficacy Assessments	Change in serum 1,25-dihydroxyvitamin D concentration, serum parathyroid hormone concentration, and blood pressure from baseline to 16-week follow-up visit.

Safety Assessment	Change in urine and serum concentrations of calcium and phosphate from baseline to 16-week follow-up visit. Research staff will assess adverse effects during the study duration by participant self-report.
Modifying Characteristics	The following characteristics will be evaluated for their influence on the biological response to cholecalciferol treatment: genetic polymorphisms, serum concentrations of vitamin D metabolic markers, race, gender, and body mass index.
Statistical Methods	Linear models will be constructed for the follow-up value of each outcome variable. Models will include the initial value of the outcome variable, treatment assignment, and the interaction of treatment with the potential modifying variables.
Date of protocol	February 5, 2018

ABBREVIATIONS

MESA = Multi Ethnic Study of Atherosclerosis

1,25(OH)₂D = 1,25-dihydroxyvitamin D, the activated form of the hormone

25(OH)D = 25-hydroxyvitamin D, the accepted marker of vitamin D storage

Vitamin D₃ = cholecalciferol, the active treatment in the study

PTH = parathyroid hormone

IU = international units

UV = ultraviolet

AE = Adverse event

SAE = Serious adverse event

GFR = glomerular filtration rate

CHSCC = Collaborative Health Studies Coordinating Center

NORC = Nutrition and Obesity Research Center

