4. PARTICIPANTS

We will conduct this vitamin D intervention study within MESA, an ethnically diverse, community-based cohort study. Up to three MESA cohorts will be approached for study recruitment. MESA originally recruited 6,814 participants in 2000-2002 from six U.S. communities: Forsyth County, NC; Northern Manhattan and the Bronx, NY; Baltimore City and [name]; St. Paul, MN; Chicago, IL; and Los Angeles County, CA. MESA Family participants are mainly siblings and parents of MESA Classic participants who were recruited in 2004-2006 for genetics-based studies. MESA Air New Recruit participants were recruited in 2006-2007 from three areas in Rockland County, NY; Riverside County, CA; and Coastal Los Angeles, CA. MESA oversampled by race/ethnicity to create a cohort that was approximately 40% White/Caucasian, 30% Black/African-American, 20% Spanish/Hispanic/Latino, and 10% Asian, primarily Chinese. All MESA Classic and Air New Recruit participants were free of clinical cardiovascular disease at the start of the study. Follow-up MESA examinations occurred 1.5, 3, 5, and 10 years after the baseline exam. A 15-year follow-up study visit (“MESA exam 6”) is ongoing and serves as the source population for this vitamin D trial.

We will recruit a total of 1,600 MESA study participants from five MESA field centers: Wake Forest University, Winston-Salem, NC; Columbia University, New York, NY; Northwestern University, Evanston, IL; University of California Los Angeles, Los Angeles, CA; and Johns Hopkins University, Baltimore, MD. MESA Classic Participants will be recruited at the time of their 6th MESA study examination, scheduled from September 2016 - March 2018. MESA Air and MESA Family participants will be recruited either during follow-up phone calls, or during a MESA INVITE-specific recruitment phone call. Inclusion criteria are active participation in MESA at one of the five field centers and willingness to participate in a clinical trial.

Exclusion criteria

1. Current use of >1,000 international units (IU) of cholecalciferol daily
2. Current use of any activated vitamin D product (calcitriol, paricalcitol, hectorol)
3. Known history of allergy or adverse reaction to vitamin D treatment
4. Known clinical history of primary hyperparathyroidism
5. Known clinical history of kidney stones within the previous 5 years
6. Current or previous history of maintenance kidney dialysis or kidney transplantation

7. Known clinical history of sarcoidosis

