8. Self-reported history of having elevated serum calcium levels
9. Serum calcium level >11 mg/dl at MESA Exam 1 (2000-2002)
10. Current participation in another interventional study
11. Inability to provide written informed consent

Standard over the counter vitamin D supplements and multivitamins typically contain between 400-800 IU of vitamin D₃ and *will be allowed* during this trial. If participants are taking >1000 IU of vitamin D daily but would like to participate in INVITe, they may participate if they reduce their total vitamin D supplement dose (from all vitamin D-containing supplements combined) to 1000 IU or less for at least 12 weeks prior to enrollment. Study staff will request that interested participants ask their health care provider whether it is safe for them to temporarily reduce their vitamin D supplement(s). Participants who temporarily reduce their vitamin D supplement(s) will wait at least 12 weeks from their last higher than 1000 IU vitamin D supplement dose prior to completing their baseline INVITe study visit. They can continue to take a total vitamin D supplement dose of up to 1000 IU daily (including 1000 IU daily) during both the 12-week temporary reduction and the 16-week study drug periods.

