7. OUTCOMES

7.1. *Change in serum 1,25(OH)₂D concentration.* 1,25(OH)₂D is the active vitamin D hormone that mediates biological effects through binding to the intracellular vitamin D receptor. The conversion of cholecalciferol to 1,25(OH)₂D and catabolism of 1,25(OH)₂D proceed through a series of metabolic steps that plausibly vary across individuals. Serum 1,25(OH)₂D will be measured at baseline and 16-weeks using our established high performance liquid chromatography-tandem mass spectrometry assay.

7.2. *Change in serum PTH concentration.* PTH is a classic response marker for vitamin D. PTH gene expression is directly suppressed by 1,25(OH)₂D and is variably suppressed by cholecalciferol, providing an ideal opportunity to assess potential genetic, biomarker, and clinical characteristics that explain differences in the response to cholecalciferol treatment. Serum PTH will be measured at baseline and 16-weeks using an automated two-site sandwich immunoassay.

7.3. *Change in blood pressure.* 1,25(OH)₂D directly suppresses the expression of renin and lowers blood pressure in experimental models. However, in humans, cholecalciferol treatment has variable effects on blood pressure, with no net difference observed in a recent clinical trial. We will explore inter-individual differences in blood pressure response to cholecalciferol treatment as a clinically relevant study outcome among a subset of study participants who are either (1) not taking anti-hypertensive medications, or (2) report no changes in anti-hypertensive medications over the 16-week study period. Three systolic and diastolic blood pressures will be obtained five minutes apart using an automated cuff with the participant seated. The average of the last two measurements will be used for analysis.

7.4. *Change in urine and serum calcium concentrations.* Vitamin D increases gastrointestinal calcium absorption. Some of the absorbed calcium deposits within bones and extraosseous tissues, but the majority is excreted in the urine. We will evaluate changes in urinary calcium excretion and serum calcium concentrations as safety outcomes and we will investigate genetic, biomarker, and clinical characteristics that may modify the effect of cholecalciferol treatment on these outcomes. Spot urine calcium to creatinine ratios, a marker of urinary calcium excretion, and serum calcium concentrations will be measured at baseline and 16-weeks using a Beckman-Coulter clinical chemistry analyzer.

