10. ANALYTIC PLAN

We will describe MESA participants screened, enrolled, and completing this ancillary study according to CONSORT guidelines and compare characteristics of participants who do and do not pass through each of these stages. Primary analyses will include participants who complete baseline and 16-week follow-up regardless of adherence. Secondary analyses will include all consented participants using multiple imputation to address data missing from the 16-week follow-up visit.

We will construct linear models for the follow-up value of each outcome variable to determine whether common and rare polymorphisms in six candidate genes modify vitamin D₃ treatment effects: *CYP2R1*, *CYP24A1*, *CYP27B1*, *CYP3A4*, *SULT2A1*, and *VDR*. Independent variables in the model will include treatment group, number of minor alleles at a given locus, the interaction between treatment group and number of minor alleles, the baseline value of the outcome variable, and the following preselected precision variables: age, gender, BMI, season, and the estimated glomerular filtration rate (GFR). Given sample size limitations we will conduct primary genetic analyses among only the white and Black subgroups with potential associations carried to the Chinese and Hispanic groups. Power to detect genetic associations of common variants are shown in Table 1. Secondary genetic analyses are planned to explore all measured and imputed genetic variants with >5% minor allele frequency derived from the Affymetrix 6.0 chip and 1000 Genomes imputation using the regression framework described above.

Table 1. Power for analyses of common variants.

Minor allele frequency	All	White	Black
0.1	0.013	0.001	0.001
0.2	0.141	0.013	0.006
0.3	0.357	0.045	0.021
0.4	0.521	0.083	0.041

We will test whether race/ethnicity, gender, body mass, index, estimated GFR, and serum concentrations of 25(OH)D, bioavailable 25(OH)D, and 24,25(OH)₂D₃ modify the response to vitamin D₃ treatment using analogous regression models to those described above.

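### Serum calcium is a safety outcome analysed only as a continuous variable; a descriptive count of high values by arm should be added

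*Combined protocol and SAP*

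**What the plan says.** **Outcome and analysis.** The Safety Assessment row of the Protocol Summary reads "Change in urine and serum concentrations of calcium and phosphate from baseline to 16-week follow-up visit". Section 7.4 adds "We will evaluate changes in urinary calcium excretion and serum calcium concentrations as safety outcomes", measured at baseline and 16 weeks. The analysis in section 10 is "We will construct linear models for the follow-up value of each outcome variable", adjusted for the baseline value. The later Analytic Plan puts an active-arm-only analysis first and runs the treatment-interaction analysis beside it. The Protocol Summary has staff assess adverse effects by asking participants. Section 9.2 sends all adverse events to the IRB and DSMB.

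**Screening.** Exclusion 9 in section 4 removes people whose calcium exceeded 11 mg/dl at MESA Exam 1 in 2000-2002. Exclusion 8 is "Self-reported history of having elevated serum calcium levels". On the later cohorts, section 4 says "MESA Family participants are mainly siblings and parents of MESA Classic participants who were recruited in 2004-2006" and "MESA Air New Recruit participants were recruited in 2006-2007".

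**Timing.** Drug is dispensed at Exam 6 (section 12.1 B) or at the Exam 6-plus visit where baseline blood is drawn (section 8.1). It is taken until Exam 6A (section 8.2). After describing Exam 6A, section 12.1 B says "Subsequently, we will mail results of serum 25-hydroxyvitamin D and calcium testing before and after" treatment.

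**The concern.** A mean change, or an adjusted mean difference, does not say how many participants in each arm finished with a high calcium. A few large rises among several hundred people barely move a mean, and a high value without symptoms would not surface through self-report. Followed as written, the trial could report no difference in mean calcium while saying nothing about the upper tail.

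The secondary issue is the baseline value. The only measured screen is old for MESA Classic participants and, judging by entry dates, absent for the Family and Air New Recruit cohorts. No release of the baseline result during dosing is stated.

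**Working it through.** The plan gives no rate, SD or power for serum calcium, so there is no figure of its own to reproduce.

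**1. Search for a count.** The Protocol Summary and section 7.4 speak of change; the Protocol Summary and section 10 model the follow-up value. Neither the active-only analysis nor the interaction analysis is a count by arm. No on-study upper limit or definition of high calcium appears. The only numeric cut-off, 11 mg/dl, is applied to the 2000-2002 value.

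**2. Arm sizes.** The Analytic Plan expects 682 participants at 3:1. 0.75 × 682 = 511.5 and 0.25 × 682 = 170.5, taken as 512 and 170.

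**3. What a comparison of means can miss.** Suppose a fraction f of the active arm rises by 3 SD and nobody else changes (assumed). The active mean moves by 3f SD. The standard error of the difference, in SD units, is √(1/512 + 1/170) = 0.0885. Power at two-sided 5% is about Φ(3f/0.0885 − 1.96).

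| f | Mean shift (SD) | Power |
|---|---|---|
| 1% | 0.03 | 5% |
| 2% | 0.06 | 10% |
| 3% | 0.09 | 17% |

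This ignores baseline adjustment, which would raise power somewhat.

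**4. What a count would show.** With zero events among n, the exact two-sided 95% upper bound is 1 − 0.025^(1/n). The missing-sample rates are assumptions.

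| Missing Exam 6A sample | Active: n, bound | Placebo: n, bound |
|---|---|---|
| 0% | 512, 0.72% | 170, 2.15% |
| 10% | 461, 0.80% | 153, 2.38% |
| 20% | 410, 0.90% | 136, 2.68% |

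If the true rate of high values were 0.2% to 2% (assumed), the active arm would be expected to contain 512 × 0.002 = 1.0 to 512 × 0.02 = 10.2 cases. The chance of seeing at least one, 1 − (1 − rate)^512, is 64% to more than 99.9%.

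**5. A count is not a test.** For 1% on placebo against 3% on active, power at two-sided 5% is about 25%. The table can describe each arm; it cannot settle a difference.

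**6. Age of the screen.** Exam 1 ran from July 2000 to August 2002 (section 12.1 A), Exam 6 began in September 2016 (section 4), and enrolment was to close on 18 January 2019 (Analytic Plan). End of August 2002 to September 2016 is 14.0 years; July 2000 to January 2019 is 18.5 years. Family and Air New Recruit participants entered after Exam 1 ended.

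**7. Timing and reach of the secondary point.** Exam 6A falls at 16 ± 4 weeks, that is 12 to 20, and the bottle holds 20 weeks of drug, so the mailing follows the planned last dose. On 1 September 2018, 682 − 523 = 159 participants (23%) were still to enrol, about 0.75 × 159 = 119 of them to active drug. If 0.2% to 2% entered with high calcium (assumed), that is roughly 0.2 to 2.4 people, plus any among those still on drug.

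**The case against.** The protocol gives good reasons for little worry. Section 12.1 D says this dose does not generally affect serum calcium and puts the concern with urinary calcium and stones. Section 9 reports no difference in adverse-event frequency in earlier trials, though some saw a small calcium rise. Other vitamin D supplements are capped at 1,000 IU daily, so supplemental intake is at most 2,000 + 1,000 = 3,000 IU, below the 4,000 IU upper limit that the protocol cites. The exclusions for self-reported high calcium, primary hyperparathyroidism, sarcoidosis, recent stones and activated vitamin D apply to every cohort. A descriptive table can also be added at reporting without a protocol change, and its absence alters no primary conclusion. All of this stands, and it keeps the point small. It does not supply the missing summary: the plan names the outcome as a safety outcome and then describes only analyses of its average.

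A reader might infer more from the baseline part: that nobody sees a high entry value until dosing has ended, or that the DSMB is never told of high values. The documents support neither. The passage in section 12.1 B describes a mailing to participants; it does not say when the laboratory, the sites or the DSMB see results. The DSMB charter and any laboratory alert procedure are not among these documents, and section 6.5 gives the DSMB a role in stopping for safety. Nor can one conclude that Family and Air participants entered unscreened, because the history-based exclusions cover them.

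**Conclusion.** The point holds as a minor one. The stated analysis of a named safety outcome is continuous only and could miss a few symptomless high values; a count by arm is a better summary for that purpose, from data already planned. The size of the gap rests on assumed fractions and shifts (1% to 3% of the active arm rising by 3 SD), since the documents give no rates. The value of the count is descriptive: bounds of about 0.7% and 2.1% at zero events with full follow-up.

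The baseline part is a question for the sponsor, not a demonstrated flaw in conduct. That the two later cohorts lack an Exam 1 value is inferred from the cohort dates in section 4; section 12.2 loosely places all MESA enrolment in 2000-2002, and the number of Family and Air participants enrolled is not given.

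**What to change.** **Main change, section 7.4.** Beside the continuous analysis, report the number and percent of participants whose Exam 6A serum calcium exceeds a limit fixed before unblinding, for example 11 mg/dl, the cut-off the protocol already uses. Show it by randomized arm, among all with a sample, with exact 95% confidence intervals, labelled as a descriptive safety summary and not a powered comparison. Cost: one extra table. It covers all participants with a follow-up sample, however long ago they enrolled.

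**Question to the sponsor, section 8.1.** Does a laboratory alert procedure already cover baseline calcium? If so, citing it is enough. If not, send baseline values above the same limit to the site investigator during dosing. Same-day dispensing can stay, no extra visit or blood draw is needed, and a pre-treatment value does not reveal the arm. The cost is faster turnaround with smaller assay batches, some site time, and possibly a few early stops of study drug. The sponsor would need to set the turnaround time and the clinical response.
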